**Table 6: Safety OPC**

Adverse Event	OPC
Thromboembolism	2.5
All Hemorrhage	1.4
All Perivalvular Leak	1.2
Endocarditis	1.2

More specifically, a statistical test based on the Poisson [9] distribution will be performed for each of these adverse event rates to evaluate whether it is less than 2 times the appropriate OPC. Thus, the null and alternative hypotheses for each adverse event are as follows:

$$H_0: \lambda \geq 2 \cdot OPC$$

$$H_A: \lambda < 2 \cdot OPC$$

where  $\lambda$  is the linearized yearly rate for the given adverse event (thromboembolism, valve thrombosis, all hemorrhage, all perivalvular leak, and endocarditis) computed when the total subject years reaches 808 and *OPC* denotes the relevant OPC. The test statistic for each adverse event is of the form:

$$Z = (\lambda - 2 \cdot OPC) / \sqrt{\lambda} .$$

$H_0$  is rejected in favor of  $H_A$  if  $Z$  is less than -1.645, the lower 5% percentile of the standard normal distribution. Grunkemeier, et al. [10] have demonstrated that 800 subject life-years is adequate to test against the smallest OPC of 1.2% per subject year (excluding valve thrombosis, and

---

PROPRIETARY DATA: This document and the information contained herein may not be reproduced, used or disclosed without written permission from Edwards Lifesciences LLC.

stratification for major versus minor hemorrhage, and perivalvular leak) with Type I and Type II error controlled at the .05 and .20 levels, respectively.

The proposed subject enrollment is calculated to ensure that at least 101 subjects survive to 8 years post implant. These  $8 \times 101 = 808$  life years in addition to the life years from those subjects not surviving to 8 years will more than fulfill the 800 life-years required by Grunkemeier, et al [10].

Sample size calculation for primary effectiveness endpoint is based on a test of the hypothesis:

$$H_0: p \leq 75\%$$

$$H_A: p > 75\%$$

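### Section 11.1's claim that 800 subject-years hold Type I and Type II error at .05 and .20 for the 1.2% OPC is narrowly missed: no fixed event cut-off strictly meets both at 800 or 808 subject-years

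*Combined protocol and SAP*

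**What the plan says.** Section 11.1 (Sample Size) bases the sample size on the four primary safety rates. Table 6 gives their OPCs as 2.5 (thromboembolism), 1.4 (all hemorrhage), 1.2 (all perivalvular leak) and 1.2 (endocarditis), in percent per subject-year.

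- **Test.** Below Table 6, each rate gets its own Poisson-based test, whose aim is "to evaluate whether it is less than 2 times the appropriate OPC". The null is rejected if Z "is less than -1.645, the lower 5% percentile of the standard normal distribution".
- **Exposure.** The rate is "computed when the total subject years reaches 808".
- **Power.** The only statement for primary safety is that a cited paper showed "800 subject life-years is adequate to test against the smallest OPC of 1.2% per subject year". After a parenthesis on what is left out, the same sentence describes this as being "with Type I and Type II error controlled at the .05 and .20 levels, respectively".
- **Extra exposure.** The 808 years from 101 eight-year survivors, "in addition to the life years from those subjects not surviving to 8 years will more than fulfill the 800 life-years required".

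The section gives no event cut-off and no true rate at which Type II error is .20.

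**The concern.** Two of the four primary safety endpoints carry the 1.2% OPC, so this sentence is their whole design justification. Event counts are whole numbers, so a fixed cut-off can offer only certain pairs of error and power. If the stated pair is not among them at the planned exposure, one of the two error rates is not as described.

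The practical stake is the pass rule. With no cut-off written down, 12 or 13 events of endocarditis or perivalvular leak at 808 subject-years would pass or fail depending on which Poisson approximation is used.

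**Working it through.** **Inputs.** From section 11.1: OPC 1.2% per subject-year; null rate 2 × 1.2% = 2.4%; one-sided 5%; exposure T = 800 (cited) or 808 (analysis). Assumption: power is evaluated at a true rate equal to the OPC, since the plan gives only the composite alternative of a rate below 2 × OPC.

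**Trying to reproduce .05/.20 at 800.** Expected events are 0.024 × 800 = 19.2 under the null and 0.012 × 800 = 9.6 at the OPC.

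- Normal approximation with null and alternative variances: Φ[(19.2 − 9.6 − 1.645√19.2)/√9.6] = Φ(0.77) = 78.0%. Reaching 80% needs about 836 subject-years.
- Square-root transform: Φ[2(√19.2 − √9.6) − 1.645] = Φ(0.92) = 82.2%. Reaching 80% needs about 751.

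The cited 800 lies between these two, so it is close to what approximations give.

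**Exact check.** Pass if X ≤ c, with error = P(X ≤ c | 0.024T) and power = P(X ≤ c | 0.012T), X Poisson.

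| T | Null mean | Mean at OPC | c | Error | Power |
|---|---|---|---|---|---|
| 800 | 19.2 | 9.6 | 11 | .0315 | .741 |
| 800 | 19.2 | 9.6 | 12 | .0556 | .828 |
| 808 | 19.392 | 9.696 | 11 | .0288 | .731 |
| 808 | 19.392 | 9.696 | 12 | .0511 | .819 |
| 808 | 19.392 | 9.696 | 13 | .0845 | .886 |
| 811 | 19.464 | 9.732 | 12 | .0495 | .816 |

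At 800 and 808, 11 events is the largest cut-off with error at or below .05, and its power is below .80. The first whole number of subject-years with both limits met is 811. Power then moves in steps: it falls to 76.0% at 860 and 78.9% at 910, and stays at or above 80% only from 912.

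**The printed Z.** On the count scale with observed variance, Z = (x − 19.392)/√x at 808. For x = 13, Z = −6.392/3.606 = −1.77, a pass; for x = 14, Z = −1.44, a fail. The implied cut-off is therefore 13, with error 8.4% and power 89%. With null variance, x = 12 gives −7.392/4.404 = −1.68, so the cut-off is 12.

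**Other endpoints at 808, held to 5%.** Hemorrhage (null mean 22.624, mean at OPC 11.312): c = 14, error 3.7%, power 83%. Thromboembolism (40.4 and 20.2): c = 29, error 3.8%, power 98%. Neither is short.

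**Sensitivity to the true rate.** With c = 11 at 808, power is 81.4% at 1.1% per year and 88.2% at 1.0%.

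**If all follow-up is used.** Assume 225 subjects, 60% eight-year survival, 15% loss over eight years and constant hazards. The combined hazard is −ln(0.60 × 0.85)/8 = 0.0842 per year, and exposure is 225 × (1 − 0.51)/0.0842 ≈ 1,310 subject-years. For the 1.2% OPC, c = 21 at 1,300 gives 92.7% power; c = 22 at 1,309 gives 95.0%.

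**The case against.** The strongest reply is that this is Poisson discreteness rather than missing exposure. At 808, a cut-off of 12 misses 5% by 0.0011. To the two decimals the plan prints, that is .05 with power above 80%, and three more subject-years remove the miss. A randomised test of exactly 5% size would have 80.8% power at 800 and 81.5% at 808. Mid-P and null-variance calculations at 808 also accept 12 events. The plan calls for an exact test for NYHA class but not here, and the cited paper's method and design alternative cannot be checked from the documents. Most of this stands, and it limits the weight of the point. It does not make the sentence exact: no randomised test is planned, and at 800, the exposure the sentence names, a cut-off of 12 has 5.6% error.

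A reader might infer that a valve performing exactly at the OPC would fail each of these two tests about 27% of the time instead of 20%. The documents do not support that. It would follow only from an exact rule of 11 or fewer events, which the plan does not specify. The printed Z on counts with observed variance passes up to 13, so on that reading the plan misses on Type I error, not on power.

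A reader might also infer that the study is too small. Section 11.1 expects life-years beyond 808, and section 11.2 includes all data up to explant or death. The instruction to compute at 808 sits uneasily with that, which makes the analysis exposure a matter to clarify.

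**Conclusion.** The point holds as a minor correction. With the true rate taken as the OPC, the stated pair of error rates is not strictly available from any fixed cut-off at 800 or 808 subject-years for perivalvular leak and endocarditis. The miss is small in exposure (811 against 808) but visible once a rule is chosen: power about 7 points under 80% if error is strictly held, error 0.1 point over 5% with one more event allowed, or 3.4 points over with two more.

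The arithmetic is firm. The conclusion rests on one unstated assumption, the true rate: at 1.1% per year the strict rule at 808 already exceeds 80% power. It also rests on reading 808 as the exposure at analysis; under the assumed survival and loss, full follow-up would give ample power. Nothing here shows that the study is underpowered or invalid.

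**What to change.** In section 11.1, replace the sentence on .05 and .20 with three items: the true rate assumed for power, the exposure at which the test is run (808 or all accrued), and the exact Poisson cut-off with its error and power for each endpoint.

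- **If 808 is kept and error is strictly held to 5%:** perivalvular leak and endocarditis pass at 11 or fewer events (2.9%, 73%), hemorrhage at 14 or fewer (3.7%, 83%), thromboembolism at 29 or fewer (3.8%, 98%), with power at a true rate equal to the OPC.
- **If all follow-up is used:** state the cut-off for that exposure, with power for the 1.2% OPC of about 93–95% near 1,300 subject-years and the survival and loss assumptions alongside.

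Section 11.3.1 refers back to this test and should follow the same rule. For the 1.2% OPC, 80% power should not be claimed at an exposure below 912 without checking the exact cut-off.

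The cost is wording only. Stated power becomes less favourable for two endpoints if 808 is kept; no extra patients are needed.

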# 1. CARPENTIER-EDWARDS® PERIMOUNT® MAGNA EASE™ PERICARDIAL BIOPROSTHESES STUDY SUMMARY

Protocol No:	2007-08
Study Title	Carpentier-Edwards Perimount Magna Ease Pericardial Bioprosthesis in the Aortic Position, Model 3300TFX
Study Purpose:	To evaluate the long term safety and effectiveness of the Carpentier-Edwards® PERIMOUNT® Magna Ease™ Valves in patients undergoing isolated aortic valve replacement.
Study Device:	Carpentier-Edwards® PERIMOUNT® Magna Ease™, Model 3300TFX.
Study Design:	This is a prospective, single-arm, multi-center study to be conducted in the US, and outside the US (OUS). This study will enroll a minimum of 225 patients implanted with the study valve in order to achieve 101 aortic valve replacement subjects each followed for a minimum of 8 years.
Study Population:	Male and female patients, 18 years or older, requiring replacement for a diseased, damaged, or malfunctioning natural or prosthetic aortic valve.
Entry Criteria:	Patients will preoperatively sign the patient informed consent form, and meet all inclusion criteria and none of the exclusion criteria to participate in this clinical study.
Duration of Participation:	After valve implantation, patients will be followed and assessed at discharge, 6-months, one year, and annually thereafter for a minimum of 8 years.
Clinical Endpoints:	
Primary Safety
 
Linearized yearly rates of:
 
 
• Thromboembolism
 
• All hemorrhage
 
• All perivalvular leak
 
• Endocarditis
 
 
Secondary Safety
 
Early rates, late linearized rates, and actuarial rates of:
 
 
• Thromboembolism
 
• Valve thrombosis
 
• All hemorrhage
 
• Major hemorrhage
 

PROPRIETARY DATA: This document and the information contained herein may not be reproduced, used or disclosed without written permission from Edwards Lifesciences LLC.

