## 5. STUDY DESIGN

This is a prospective, single-arm, multi-center study to be conducted in the US and outside the US (OUS). A minimum of 225 subjects will be implanted (Section 11.1 Sample Size) to obtain long term data from 101 subjects at 8 years post implant of the Carpentier-Edwards PERIMOUNT

Magna Ease Pericardial Aortic Bioprosthesis, Model 3300TFX (Magna Ease valve). Subject enrollment will not start in the US before obtaining FDA approval of this post approval study.

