where  $p$  is the proportion of the subjects in NYHA Class I or Class II at 8 years post implant. The expected proportion of the alive subjects in NYHA class I or II at eight years is above 90%, based on 8 year follow up data for the Carpentier-Edwards PERIMOUNT 2700/2800/2900 valve (this proportion is above 90% within the subjects with valid NYHA assessment at each annual visit till 8 years follow up). Based on this expected proportion, a sample size of 45 subjects provides 85% power to test the hypothesis that the true proportion is greater than 75% using an exact binomial test. Thus, the sample size of 101 subjects with NYHA data at 8 year post implant is more than adequate to provide sufficient power.

The calculated number of subjects ( $n$ ) that must be enrolled in order to have 101 subjects survive to 8 years post implant with 99% probability is based on the binomial distribution. Specifically,  $n$  is such that

$$1 - \sum_{x=1}^{101} \binom{n}{x} p^x (1-p)^{n-x} > 99\%$$

where  $p$  is the probability that a subject will survive for 8 years post implant. This calculation can be performed using standard statistical software. Based on the reported 8-year survival of 60% from Aupart, et al. (2006) [8], a sample size of 195 subjects fulfills the requirements of the equation above. Based on the data collected in a previous post approval study conducted by

---

PROPRIETARY DATA: This document and the information contained herein may not be reproduced, used or disclosed without written permission from Edwards Lifesciences LLC.

Edwards (Study 98-1), a lost to follow-up rate of 7.8% was observed among subjects who reached 5 or more years of follow-up post implant. The sample size is further inflated to 225 to account for up to a 15% rate of lost to follow up.

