## **11.4 EFFECTIVENESS ANALYSIS**

### **Subject functional classification**

Subjects will be stratified according to the NYHA classification preoperatively, at 6 months and annually post implant for 8 years. The distribution (numbers of subjects and percentages) in the various NYHA classes will be tabulated at each follow-up interval.

The primary effectiveness analysis will include all the subjects who survived the implant procedure and have at least one post-implant NYHA assessment. The proportion of the subjects in NYHA Classes I and II at 8 years post implant will be calculated to determine if it is  $\geq 75\%$  using a one-sided Binomial exact test. For subjects who die, withdraw or are lost to follow-up before reaching the 8 year follow-up visit, the last observed NYHA classes will be used in this analysis. As a consequence, those subjects will be counted as failures if they were in NYHA Classes III or IV at the time those events occurred. Subjects whose status at the time of the events is not known will be counted as failures if they were in NYHA Classes III or IV during their last assessment prior to the time of the events.

The proportion of subjects in NYHA Classes I and II and proportion of subjects who died and were in NYHA Classes III and IV at death or at their last known NYHA classification will also be calculated at each annual report.

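### Enrolling 225 does not cover the stated 15% loss to follow-up: it retains the required 195 only up to about 13.3% loss, and the printed summation limits do not reproduce 195 (minor, wording only)

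*Combined protocol and SAP*

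**What the plan says.** Section 11.1 (Sample Size) sets the aim: "The proposed subject enrollment is calculated to ensure that at least 101 subjects survive to 8 years post implant". It defines n as the number that "must be enrolled in order to have 101 subjects survive to 8 years post implant with 99% probability", using a binomial formula printed as one minus the sum of the terms x = 1 to 101. With 60% survival at 8 years, it reports that "a sample size of 195 subjects fulfills the requirements of the equation above".

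The section then turns to loss to follow-up. From an earlier post-approval study it reports that "a lost to follow-up rate of 7.8% was observed among subjects who reached 5 or more years of follow-up post implant", and it concludes: "The sample size is further inflated to 225 to account for up to a 15% rate of lost to follow up". The inflation step itself is not shown.

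Elsewhere 225 is tied to subjects observed at 8 years, not merely alive. The Study Summary (Section 1) gives 225 as the minimum "in order to achieve 101 aortic valve replacement subjects each followed for a minimum of 8 years", and Section 5 gives it as the minimum implanted "to obtain long term data from 101 subjects at 8 years post implant". Table 1 makes 101 completed 8-year assessments the milestone for completing follow-up. Under Section 10.6 withdrawn subjects are not replaced, and under Section 10.5 subjects leave the study after explant.

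**The concern.** An allowance for loss has to leave the required number after the loss has happened. Taking 15% away from 225 leaves fewer than the 195 that the plan has just shown it needs, so the sentence credits 225 with a property it does not have.

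Two further gaps make the sentence hard to check. The plan does not define the 15%: the text does not say whether it is a share of those implanted or a share of those who would otherwise be seen at 8 years, and the 7.8% it cites refers to a selected group. Also, the formula as printed does not yield 195, so a reader who follows it literally cannot reproduce the starting figure.

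At stake is whether the sample-size justification is true and reproducible, and how firmly the plan can promise 101 subjects with 8-year data.

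**Working it through.** **Inputs, all from Section 11.1:** target of at least 101; assurance of 99%; 8-year survival p = 0.60; n = 195 before loss; loss allowance of 15%; n = 225 after inflation; earlier observed loss of 7.8%.

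**1. Reproduce 195.** With X ~ Binomial(n, 0.60), the aim is P(X ≥ 101) > 0.99.
- n = 194: 0.98965
- n = 195: 0.99166

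So 195 is the smallest n that meets the stated aim.

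**2. Check the printed limits.** One minus the sum over x = 1 to 101 is P(X ≥ 102), apart from a negligible x = 0 term.
- n = 195: 0.98777 (98.78%), which fails
- n = 196: 0.99011, which passes

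The limits for at least 101 are x = 0 to 100, and these return 195.

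**3. Reproduce 225.** 195 × 1.15 = 224.25, which rounds up to 225. This multiplies by one plus the loss rate. Retaining 195 after 15% loss requires division: 195/(1 − 0.15) = 229.4.

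**4. What 225 retains.** 225 × 0.85 = 191.25, below 195. The loss at which 225 still leaves 195 in expectation is 1 − 195/225 = 13.3%.

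**5. Carry the 99% through (inference).** Let L be the probability that an 8-year survivor is not followed to 8 years, independent of death, with no explant exits. The number followed to 8 years is then Binomial(225, 0.60 × (1 − L)).

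| L | Expected count | P(at least 101) |
|---|---|---|
| 7.8% | 225 × 0.60 × 0.922 = 124.5 | 99.9% |
| 12.6% | 225 × 0.60 × 0.874 = 118.0 | 99.0% |
| 13.3% | 117.0 | 98.6% |
| 15% | 225 × 0.60 × 0.85 = 114.75 | 97.1% |

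The 13.3% in step 4 and the 12.6% here answer different questions. The first keeps 195 on average. The second keeps the 99% probability when the number lost is itself random.

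**6. Consequences for the analyses at L = 15%.**
- Subject-years: the expected 114.75 subjects followed to 8 years alone contribute 114.75 × 8 = 918, above the 800 required. Adding partial follow-up, under constant hazards (an assumption), the mean is about 1,310.
- NYHA test: the count assured with 99% probability is 97. An exact one-sided 0.05 test of 75% with 97 subjects rejects at 81 or more and has power 0.984 at a true 90%.

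**The case against.** The strongest reply is that the plan attaches 99% only to survival. For survival alone, 225 gives more than 99.999%. The inflation sentence does not repeat the 99%, and Sections 1 and 5 state the target of 101 without a probability. At 15% loss the expected count of about 115 still exceeds 101, and 225 is a minimum, so more may be enrolled. This stands as far as the 97.1% and 12.6% figures go: they depend on carrying the criterion over, which is an inference. It does not rescue the sentence, because 191.25 falls short of 195 without any reference to 99%.

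It can also be said that multiplying by 1.15 is a common convention and that the gap is about five subjects. That is true, and it is why the point is minor.

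On the formula, Section 11.1 already states the intent as at least 101, and correcting the limits leaves both 195 and 225 unchanged. That is also true; the defect is only that the printed equation and the reported number disagree.

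Two stronger readings are tempting. A reader might infer that the trial is too small and that enrolment must rise to 230 or more. The documents do not support this: no test or subject-year target depends on the missing five subjects, and the observed 7.8% is well inside what 225 covers. A reader might also take 15% as the share of all implanted subjects recorded as lost before death and compute a lower probability. That needs a model of loss against death over time, which the documents do not contain, so no such figure is given here.

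**Conclusion.** The stated allowance is wrong as written, and the effect is minor. The retention result (191.25 against 195, covered to about 13.3%) is plain arithmetic on the plan's own numbers. The probability results (97.1% at 15% loss, 99% up to about 12.6%) rest on four assumptions: 60% survival at 8 years, loss and withdrawal combined being independent of death, no explant exits, and the 99% criterion applying to subjects followed to 8 years.

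The shortfall is smaller than the uncertainty in the survival input: at 61.7% survival and 15% loss, 225 gives 99.0%.

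Explant exits would lower all these probabilities. By how much cannot be fixed from the documents. The only explant figure is in Section 9: 85.1% freedom from explant due to valve dysfunction at 14 years, for a predecessor valve.

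The primary analyses are not endangered. The NYHA test holds both under Section 11.4, where for early exits "the last observed NYHA classes will be used in this analysis", and under the available-data analysis that Section 11.6 also requires, given the power shown above.

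**What to change.** Keep 225 and revise the wording of Section 11.1 as follows.

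1. State that 225 retains the required 195 up to about 13% loss.
2. State that, assuming 60% survival at 8 years, loss and withdrawal combined independent of death, and no explant exits, 225 gives at least 99% probability of 101 subjects followed to 8 years up to about 12.6% loss, and about 97% at 15%.
3. Define loss as the probability that an 8-year survivor is not followed to 8 years.
4. Note that exits after explant (Section 10.5) would lower these figures, and that the only documented explant figure is the predecessor-valve result at 14 years in Section 9.
5. Print the summation limits as x = 0 to 100, which reproduces 195.

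The cost is text only: no added subjects and no change to any endpoint, test or analysis population. The stated allowance becomes slightly less favourable. Under Section 17.3 the change needs a written amendment agreed by FDA, unless it is accepted as administrative and reported in the Annual Report.

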## 11.2 ANALYSIS POPULATION

All the data collected up to the point of the explant or expirations will be included in the safety and effectiveness analyses. The primary safety analysis will include all the enrolled subjects. The primary effectiveness analysis will include the subjects who survived post implant and have at least one post-implant NYHA assessment.

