#### **4.2.2 SECONDARY SAFETY ENDPOINTS**

Descriptive information of early rates, late linearized rates and actuarial analysis of the following:

- Thromboembolism
- Valve thrombosis
- All hemorrhage
- Major hemorrhage
- All perivalvular leak
- Major perivalvular leak
- Endocarditis
- Hemolysis
- Structural valve deterioration

- Non-structural valve dysfunction
- Reoperation
- Explant
- Death
- Valve-related death

Blood Data (white blood count, red blood count, hematocrit, hemoglobin, platelet count, serum lactate dehydrogenase, haptoglobin and reticulocytes).

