### 10.4 AUTOPSY/DEATH

Copies of the autopsy report and/or death summary must be sent to Edwards as permitted by local laws. This information should be redacted at the site to remove any identifying information (i.e. subject full name, personal identification numbers, address, etc.). Information on the cause of death and valve relatedness will be evaluated by the Principal Investigator.

Deaths which must be reported to Edwards Clinical Affairs Department include:

- All deaths while participating in the study.
- All deaths up to 30 days post study valve explantation.

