### 10.5 EXPLANTED VALVES

Every effort should be made to return the explanted valve(s), at autopsy or explantation to Edwards. The explanted valve should be placed in a container with a suitable histological fixative such as 10% formalin or 2% glutaraldehyde immediately after excision and returned to Edwards. Refrigeration is not necessary under these circumstances. Contact Edwards Clinical Research for additional instructions.

Any pertinent information, e.g. operative notes, autopsy report etc should be sent to Edwards. This information should be redacted at the site to remove any identifying information (i.e. subject full name, personal identification numbers, address, etc.).

After the study valve is explanted, the subject will be followed for either an additional 30 days to monitor for any new adverse events or until all study device related serious adverse events (see section 9.1) are resolved. After that point the subject will be discontinued from the study. No further evaluations and/or case report forms are needed after study exit. Data from these subjects will be included in analysis.

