### **Time to Death, Reoperation, and Explant**

Time to death from the date of operation will be analyzed by the method of Kaplan and Meier. Time to reoperation from the date of operation as well as time to explant from the date of reoperation will be similarly analyzed. For time to explant and time to reoperation, the time to *first* explant or reoperation will be calculated for those subjects requiring explant or reoperation. These analyses will also be reported stratified by valve size. Analyses for time to explant and time to reoperation will also be stratified by fatal versus non-fatal events.

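### Section 11.2 ends the analysed data at explant, which conflicts with the post-explant collection in 10.4 and 10.5 and the fatal/non-fatal split in 11.3.2; applied as written, it would leave deaths soon after explant out of the death endpoints

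*Combined protocol and SAP*

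**What the plan says.** The only general rule on which data enter the analyses is in section 11.2: "All the data collected up to the point of the explant or expirations will be included in the safety and effectiveness analyses".

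Three other sections bear on the time after explant.

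- Section 10.4 lists the deaths that must be reported. Besides all deaths during participation, it names "All deaths up to 30 days post study valve explantation".
- Section 10.5 says "After the study valve is explanted, the subject will be followed for either an additional 30 days to monitor for any new adverse events". The alternative end that it gives is the resolution of device-related serious adverse events. The subject then leaves the study. The paragraph ends: "Data from these subjects will be included in analysis". No time limit is attached to that sentence.
- Section 11.3.2, under time to death, reoperation and explant, says "Time to death from the date of operation will be analyzed by the method of Kaplan and Meier" and gives no censoring rule at explant. It adds: "Analyses for time to explant and time to reoperation will also be stratified by fatal versus non-fatal events". It does not define a fatal explant or reoperation.

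Death and "Valve-related death" are secondary safety endpoints in section 4.2.2, which describes that whole list as descriptive.

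**The concern.** The natural reading of 11.2 is a cut at explant; if later data were meant to count as well, naming explant as an end point would serve no purpose. The study nevertheless goes on collecting deaths and adverse events after explant, states that these subjects are analysed, and plans an analysis that needs to know whether an explant was fatal.

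Death after removal of a failed or infected prosthesis is among the most serious consequences of valve failure. If it falls outside the data set, the subject contributes an explant but no death. In a Kaplan-Meier analysis that subject would be censored at the start of a second heart operation, when the risk of death is plausibly raised. Such censoring is informative and would make survival and freedom from valve-related death look somewhat better than they are. Two analysts following the plan could report different counts. If the choice is made after the events are known, it is open to the criticism that the results guided it.

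**Working it through.** **Reading the rules together.** Take a subject whose study valve is explanted and who dies five days later.

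- Section 10.4: the death must be reported.
- Section 10.5: the subject is still in follow-up, and the data are to be included in analysis.
- Section 11.2: the death comes after the explant, so it lies outside the data described there.
- Section 11.3.2, time to death: a death on day 5 if 10.5 governs. If 11.2 governs, no death is counted and the natural consequence is censoring at explant.
- Section 11.3.2, fatal/non-fatal split: a fatal explant if the death is in the data set; otherwise the explant can only be classed as non-fatal. A death during the explant operation itself could still count under 11.2, which names death as well as explant as an end point.

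The two readings give different answers for the same subject, and no section sets an order of precedence.

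**Direction.** Leaving out such deaths can only lower the counts of death, valve-related death and fatal explant.

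**Size, first illustration.** The plan states no figure for this. The number enrolled, 225, is from section 11.1. The explant proportion (3-8% by 8 years) and the 30-day mortality after explant (5-15%) are assumptions. Deaths affected = 225 × proportion explanted × 30-day mortality.

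- Low: 225 × 0.03 × 0.05 = 0.34
- Middle: 225 × 0.05 × 0.10 = 1.1
- High: 225 × 0.08 × 0.15 = 2.7

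**Size, second illustration.** Section 9 reports 85.1% freedom from explant due to valve dysfunction at 14 years with an earlier valve model. Assume constant hazards.

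- Explant hazard = −ln(0.851)/14 = 0.0115 per year, so freedom from explant at 8 years = exp(−8 × 0.0115) = 91.2%.
- Death hazard from the 60% 8-year survival in 11.1 = −ln(0.60)/8 = 0.0639 per year.
- Subject-years = 225 × (1 − exp(−8H))/H, where H is the sum of the hazards. With death and explant, H = 0.0754, giving about 1,352. Adding 15% loss to follow-up over 8 years (−ln(0.85)/8 = 0.0203) gives H = 0.0957 and about 1,258.
- Expected explants = subject-years × 0.0115: about 16 and 14 respectively, or about 9 over the 808 subject-years that the plan takes as its minimum.
- With 5-15% 30-day mortality, the deaths affected run from 9.3 × 0.05 = 0.5 to 15.6 × 0.15 = 2.3. Widening the mortality to 2-20% gives 0.2 to 3.1.

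The two illustrations agree. The second uses another valve model and counts only explants for valve dysfunction, so it gives scale and is not a forecast.

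**Against the total.** At 60% survival, 225 × 0.40 = 90 deaths are expected. The first illustration's range is 0.34/90 = 0.4% to 2.7/90 = 3.0% of them. The share of valve-related deaths could be larger, but the documents give no expected number.

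**The case against.** The strongest defence is that 11.2 does not exclude anything. It says what will be included, does not contain the word only, and is silent on later data. The closing sentence of 10.5 comes directly after the description of post-explant follow-up and study exit, so it can be read as covering that window. The fatal/non-fatal split in 11.3.2 suggests that the authors meant to use deaths associated with explant.

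This defence stands in part. A reader might infer that the plan definitely discards these deaths, or that it directs time to death to be censored at explant. The documents support neither: no section states such censoring, and 10.5 points the other way. A reader might also infer that nearly every fatal explant would be lost. Nothing in the documents gives the timing of death after explant, a death at the operation itself could still count, and 11.2 sets no cut at a reoperation that leaves the valve in place.

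The defence does not remove the conflict. The sentence in 10.5 has no time limit while 11.2 has one, and nothing tells the analyst which prevails.

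A second objection also stands. Strokes and bleeds after a second operation, with the study valve gone, need not be charged to that valve. Ending attribution at explant is defensible for thromboembolism and hemorrhage, which are primary endpoints tested against twice the OPC. The argument for counting deaths does not carry over to those rates.

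**Conclusion.** Section 11.2 conflicts with 10.4, 10.5 and 11.3.2. Applied as written, it would leave out deaths shortly after removal of the study valve, in a direction that favours the device. The expected size is about 0.3 to 2.7 deaths, resting on assumed rates of explant and post-explant mortality that the documents do not give.

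The death endpoints concerned are secondary and descriptive. The effect on all-cause death is slight; on valve-related death and the fatal-explant stratum it could matter more, because counts there may be small. No sample size, power or primary hypothesis test depends on these death counts. The contradiction is worth resolving because the data are already required and the rule should be fixed before results are known.

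**What to change.** Amend 11.2 so that, for death, valve-related death and the fatal/non-fatal split of explants and reoperations:

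- deaths from explant to the study exit defined in 10.5 are counted at their own date; and
- time to death is not censored at explant. A subject alive after explant is censored at that study exit.

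Because 10.5 gives two possible ends to post-explant follow-up, the amended text should make clear how the exit date is determined for analysis and what makes an explant or reoperation fatal.

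State separately, endpoint by endpoint, whether thromboembolism, hemorrhage and the other device-specific event rates stop at explant. The primary OPC comparisons should not be extended past explant by default: doing so would add events after a second operation to rates meant to describe the study valve.

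The cost is a change of analysis text, with no new data collection, since 10.4 and 10.5 already require the information. The downside is that the death and valve-related death rates may be slightly less favourable.
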